#### 4.9.5. Electrocardiogram

Not applicable.

#### 4.9.6. Prior and Concomitant Medications

A concomitant medication is defined as any medication/therapy with an end date on or after the date of the first drug administration of study drug or missing (medication assumed to be ongoing).

A prior medication is defined as any medication with an end date prior to the date of the first administration of study drug.

Prior and concomitant medications will be coded using the WHO Drug Dictionary. Results will be tabulated by Anatomic Therapeutic Chemical (ATC) Level 2, Level 4) and Preferred Term.

All medications will be presented in a data listing, with a flag identifying them as prior or concomitant medications.

Type of dialysis (haemodialysis, peritoneal dialysis, none) will be summarised at each visit. All data related to dialysis will be listed.

#### 4.9.7. Subject Reported Palatability and Acceptability

Subject reported palatability and acceptability results will be summarised at each time point. By-subject listings of visual analogue scale measurements will be presented in a data listing.

#### 5. CHANGES TO PLANNED ANALYSES

To take into consideration covariate factors for the evaluation of the primary endpoint, baseline serum phosphorus, age (in categories) at randomisation, region and gender, a mixed model will be used in replacement to the paired t-test mentioned in the protocol.

Following discussions and agreements with PDCO and FDA, the following new age classification at randomisation will be used for the outputs: 0 to <1 year/ $\geq$ 1 year to <6 years/ $\geq$ 6 years to <12 years/ $\geq$ 12 years to <18 years.

Due to difficulties in the recruitment of patients below 9 years of age, PDCO agreed to reduce required minimum numbers of recruited patients as follows:

At least 60 subjects must be randomised into PA21 group and the following number of subjects from each age group as detailed below:

- Less than 1 year: no minimum number of randomised patients
- From 1 to less than 6 years: at least 5 patients on PA21
- From 6 to less than 12 years: at least 10 patients on PA21
- From 12 to less than 18 years: at least 10 patients on PA21
- Phoslyra arm: no minimum number of randomised patients.

Furthermore, FDA agreed that a partial waiver of PREA study requirements in patients less than 2 years of age can be justified on the basis that necessary studies are impossible or highly impracticable. The Agency also believes that it may be possible to generalize the findings in older paediatric patients down to younger patients greater than 2 years of age, indicating that the study can be completed without the need to recruit originally required minimum numbers of patients below 9 years of age.

Following PDCO advice from the Modification Summary Report Day 30 (EMA/170421/2018), the Sponsor plans to include additional comparison with an external control from paediatric study SVCARB07609 (EudraCT No. 2011-002329-23), conducted with sevelamer carbonate [Fathallah-Shaykh S. et al, 2018] where appropriate. This Phase II study is a 2-week, randomized, placebo-controlled, fixed dose period followed by a 6-month, single-arm, openlabel, dose titration period study to investigate the efficacy and safety of sevelamer carbonate in hyperphosphatemic paediatric patients with CKD. The Sponsor selected this external control from available studies on the hyperphosphatemic paediatric patients with CKD due to the large sample size and the results of this paediatric study supported the extension of the indication for sevelamer to paediatric patients in the EU [EMA/271022/2016 and EMA/352101/2017]. However, due to differences in the design of the studies, there will be limitations to this comparison approach.

Descriptive comparison of safety endpoints, including AE profile, using publicly available data from the SVCARB07609 trial is foreseen and will be summarised in a separate report supporting the main conclusions from the PA-CL-PED-01 study.

According to the clinical study protocol the following iron status parameters have to be assessed: Iron, Ferritin, Transferrin and Transferrin saturation (TSAT). The iron parameters assessed during the conduct of study PA-CL-PED-01 are: Iron, Ferritin, Transferrin and Unsaturated Iron Binding Capacity (UIBC).

Unsaturated iron binding capacity (UIBC) is a surrogate marker of TSAT and has been reported to identify 100% of iron overloaded patients and 95% of patients with normal iron stores. The UIBC is therefore a reliable method.

The use of UIBC instead of TSAT is estimated to have no impact on the reliability of safety assessments in this clinical study and on the conclusions of the analysis. Therefore, TSAT will not be derived and presented. A Note to File at Vifor was created.

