#### 4. STATISTICAL METHODS

# 4.1. Sample Size Justification

In the PA21 treatment group, assuming a mean change in serum phosphorus levels from baseline to end of Stage 1 of 1.2 mg/dL, a standard deviation for the change of 2.0 and to further allow for an approximate drop-out rate of 30%, 100 randomised subjects will provide more than 90% power.

The sample size estimation is based on conservative values from the Phase 3 study, and performed using nQuery Version 6.0.

One hundred subjects should also be sufficient to provide robust safety and dosing information for PA21 in the paediatric and adolescent subjects with CKD.

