#### 1. PA21

## 2. Phoslyra

A 'Total' column will be used in all the outputs, which will present a total over both treatment groups, with the exception of exposure data where data will be presented separately for each drug.

Tabulations will be produced for appropriate demographic, baseline, efficacy and safety parameters. For categorical variables, summary tabulations of the number and missing observations as well as the number and percentage within each category of the parameter will be presented. For continuous variables, the number and missing observations, mean, median, standard deviation, Q1, Q3, minimum, and maximum values will be presented.

For the laboratory parameters, the number of the decimal places (dp) will be determined using the following rules based on the number of dp from the raw data:

- mean, median, q1 and q3 = raw + 1
- sd = raw + 2
- Min and max = raw

Formal statistical hypothesis testing will be performed on the primary endpoint only with test conducted at the 2-sided, 0.05 level of significance. Summary statistics will be presented, as well as confidence intervals on selected parameters, as described in the sections below. Some other statistical tests within each group may be performed for the secondary efficacy endpoints depending on the observed clinical differences.

Baseline will be defined as the latest measurement collected prior to first dose of study treatment.

Stage 1 data will be defined as all data collected until the last visit in the titration phase (prior to visit 12 and when "Yes" is responded to the question "Will subject enter the Stage 2 Safety Extension period after the current visit?"). Of note, if subject withdrew during stage 1 (i.e. no stage 2 initiated), visit 16 will be considered as part of stage 1.

Stage 2 data will be defined as all data collected from the day after the last visit in the titration phase.

Both local and central laboratory data will be reported using SI units, unless otherwise specify.

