## 4.7.1. Primary Efficacy Endpoint

The primary efficacy endpoint is the change in serum phosphorus levels from baseline to the end of Stage 1 (i.e. considering the last available value in stage 1) in PA21 group. It is based on central laboratory data; in case of missing data regarding central laboratory data, local laboratory measurements are used (please refer to Section 4.2.8.1 for the imputation to be applied).

The change from baseline in the PA21 group will be analysed using a linear mixed model with treatment, baseline serum phosphorus, age (in categories) at randomisation, region and gender as fixed effects. Summary statistics with the estimate of the adjusted mean change from baseline and its 95%CI as well as the corresponding p-value from the t-test will also be provided.

The SAS code used for the linear mixed model will be as below:

```
proc mixed data=input method=type3;
    class treatment age region gender;
    model chg_end_stage1=treatment age region gender baseline / ddfm=KENWARDROGER solution;
    lsmeans treatment / CL alpha=0.05;
    where treatment='PA21';
    ods output lsmeans=lsm1;
```

run;

The primary efficacy analysis will be repeated on the FAS by the following subgroups:

- Formulation (tablets only/sachets only/both)
- Serum phosphorus at baseline according to the age related normal range (above, within + below; see Table 5)
- Age group at randomisation (0-<2, 2-<6, 6-<12, 12-<=18) \* Serum phosphorus at baseline according to the age related normal range (above, within + below; see Table 5). In case of no subject in an age group, this category will not be displayed.

Sensitivity analyses will include a repeat of the primary analysis on the FAS population based on observed data from the central laboratory only (with no imputation by local laboratory data).

Homogeneity of the results of the primary endpoint will be investigated on the FAS population by displaying summary statistics of change from baseline with the estimate of the adjusted mean change from baseline and its 95%CI for the following subgroups using the same linear mixed model as above:

- By age group at randomisation
- By gender
- By region

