## 4.7.2. Secondary Efficacy Endpoints

For the following secondary endpoints, summary statistics with 95%CIs for the mean change will be provided by treatment group using the same linear mixed model as for the primary efficacy endpoint:

- Change in serum phosphorus levels from baseline to the end of Stage 1 in Phoslyra group
- Change in serum phosphorus levels from baseline to the end of Stage 2 in both groups

The above secondary endpoints are based on central laboratory data; in case of missing data regarding central laboratory data, local laboratory measurements are used (please refer to Sections 4.2.8.1 and 4.2.8.2 for the imputation to be applied).

Serum phosphorus values over time will be summarised by treatment group using descriptive statistics based both on central and on local laboratory measurements, separately.

Box plots will be generated for the change in serum phosphorus levels from baseline for each treatment arm to the end of Stage 1 and to the end of Stage 2 on the FAS and PPS Populations.

In addition, plots will be provided with one curve for each treatment arm representing the mean change (±standard error of the mean (SEM)) from baseline in serum phosphorus levels at each time point to the end of Stage 1 and to the end of Stage 2 for the FAS and PPS Populations.

For the following secondary endpoints based on both central and local laboratory measurements, number and percentage calculated using the number of subjects with non-missing serum phosphorus level as denominators with corresponding exact 95%CIs will be provided by treatment group:

- Subjects with serum phosphorus level within the age related target range at each visit
- Subjects with serum phosphorus level within the age related normal range at each visit.

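### The one-arm primary model treats the sample mean baseline as a known constant, so its CI and p-value understate the sampling error of PA21's population mean change

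*SAP*

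**What the plan says.** Section 5 announces that "a mixed model will be used in replacement to the paired t-test mentioned in the protocol", so that baseline serum phosphorus, age category, region and gender are taken into account. Section 4.7.1 puts this into effect: "The change from baseline in the PA21 group will be analysed using a linear mixed model with treatment, baseline serum phosphorus", age category, region and gender as fixed effects. The code there restricts the data to PA21, has no RANDOM or REPEATED statement, enters baseline as a plain linear covariate, and requests `lsmeans treatment` with default settings. Treatment then has a single level. Its LS-mean is the fitted change at the sample mean baseline, with equal weight on each age, region and gender class.

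This is the trial's only planned formal test. Section 4.2.1 states: "Formal statistical hypothesis testing will be performed on the primary endpoint only with test conducted at the 2-sided, 0.05 level of significance". Section 4.7.2 derives the secondary CIs "using the same linear mixed model as for the primary efficacy endpoint". Section 4.1 plans the trial on "a standard deviation for the change of 2.0". The paired t-test is not kept as a sensitivity analysis; the primary analysis is otherwise repeated only on central laboratory data, on the PPS and in subgroups.

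**The concern.** In a comparison of two arms, conditioning on baseline is harmless because the mean baseline cancels from the difference. Here one arm's mean change is tested against zero. If the enrolled children happen to start above the population mean, and higher starters fall further, their mean change is larger for that reason alone. The paired t-test counts this sampling error because it uses the full SD of the change. The regression removes the part of the SD that baseline explains and puts nothing back for the uncertainty in the mean baseline. The Kenward-Roger option does not restore it, since the model has no random effect.

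A non-zero slope is likely. Change contains minus baseline by construction, and Section 2.1 has doses titrated towards age-specific targets. At stake are the nominal level of the only formal test and the coverage of every one-arm interval for change in phosphorus.

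**Working it through.** **Inputs from the SAP.** Mean change 1.2 mg/dL, SD of change 2.0, 100 PA21 subjects and about 30% dropout (4.1), hence 100 × 0.7 = 70 evaluable. Reduced floor of 60 on PA21 (Section 5), hence 60 × 0.7 = 42. Two-sided 0.05 (4.2.1).

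**Assumed, because the SAP does not give them.** R², the share of the variance of change explained by baseline, and the age and region mix. With equal SDs at both times and baseline-to-end correlation ρ, R² = (1 − ρ)/2, so ρ = 0.7, 0.5 and 0 give R² = 0.15, 0.25 and 0.5. Age, region and gender are taken as unrelated to the outcome.

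**The plan's own figure.** For a paired t-test with n = 70 the noncentrality is 1.2/(2.0/√70) = 5.02 and power is 99.9%. With n = 42 it is 3.89 and power is 96.7%. Both agree with the stated power of more than 90%.

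**Variance of the LS-mean.** Write σ for the SD of change and b for the baseline slope, so that b² Var(baseline) = R²σ². Let D be the factor by which equal class weights enlarge the variance (D = 1 for balanced groups or observed-margin weights).

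- Reported variance: Dσ²(1 − R²)/n
- Variance for the population mean change: Dσ²(1 − R²)/n + R²σ²/n
- Ratio of SEs: k = √[D(1 − R²) / (D(1 − R²) + R²)]
- True size of the nominal 5% test: 2[1 − Φ(1.96k)]

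**D for assumed mixes.** Age 12/28/60%: (1/9)(1/0.12 + 1/0.28 + 1/0.60) = 1.51. Two equal regions and equal sexes add nothing, so D ≈ 1.51. Three regions at 45/10/45%: (1/9)(2/0.45 + 1/0.10) = 1.61, which adds 0.61, so D ≈ 2.11.

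| R² | D = 1: k, size | D = 1.51: k, size | D = 2.11: k, size |
|---|---|---|---|
| 0 | 1.00, 5.0% | 1.00, 5.0% | 1.00, 5.0% |
| 0.15 | 0.92, 7.1% | 0.95, 6.4% | 0.96, 6.0% |
| 0.25 | 0.87, 9.0% | 0.90, 7.6% | 0.93, 6.9% |
| 0.5 | 0.71, 16.6% | 0.78, 12.9% | 0.82, 10.6% |

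**Simulation of the literal model** (equal weights, n = 70, 12/28/60% ages, two or three regions, true mean change 0): about 5–7%, 6–7% and 9–13% at R² 0.15, 0.25 and 0.5. These run slightly below the formula because random class sizes make D larger. A very uneven mix of four age groups and three regions (D about 4.6) gives 5.7% at R² 0.25 and 7.0% at 0.5.

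**After correction.** Adding b² Var(baseline)/n gives a simulated size of 4.3–5.5%. The paired t-test gives 4.3–5.7%.

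**Comparison with the paired-t interval** (n = 70, R² = 0.25). Balanced groups: model SE 0.213, true SD of the estimate 0.243, paired-t SE 0.238. Age split 10/25/65%: model SE 0.295, true SD 0.323, paired-t SE 0.238. The model SE is below its own true value both times, but below the paired-t SE only in the balanced case.

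**The case against.** The strongest defence is that regression intervals are conventionally conditional on the observed covariates, and on that reading this one is valid. The algebra stands, but the SAP never states a conditional target. Its primary objective (1.2) concerns paediatric and adolescent subjects with CKD, and the paired t-test that it replaces addresses the population mean change. At the least the target is unspecified.

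The size is also uncertain. R² is assumed, and because entry requires hyperphosphataemia for age (3.2), baseline variance may be restricted. If it were 60% of the unrestricted value, R² at ρ = 0.5 would fall from 0.25 to 0.17. This limits the figures, not the direction.

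Four stronger readings might be inferred, and the SAP does not support them:

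- That the type I error is about 7–16%. That range needs observed-margin weights; the code in 4.7.1 weights classes equally.
- That the SAP interval is narrower than the paired-t interval. With uneven age or region groups it is usually wider. It is too narrow only for its own estimator's sampling error.
- That a significant primary result would be spurious. At the planning values t is about 5.
- That 4.1 is wrong to plan on the SD of change, or that the switch was hidden. Planning on that SD is not an error, 4.1 names no test, and Section 5 openly discloses and explains the change.

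**Conclusion.** The point holds in this limited form. For the population mean change, the CI and p-value specified in 4.7.1 omit slope² × Var(mean baseline), so the 5% level and 95% coverage do not hold unless the slope is zero. The direction follows from the code alone. The size rests on the assumed R² and class mix: slight at R² 0.15, modest at 0.25, and roughly a doubling of the nominal error or more at 0.5. The practical damage is to interval coverage rather than to the likely conclusion of the test. It matters most in 4.7.2, where results are reported mainly as intervals. This should be corrected but does not undermine the trial.

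**What to change.** In 4.7.1 and 4.7.2, keep the covariate model but take the CI and p-value from a variance that adds slope² × Var(baseline)/n to the LS-mean variance, or from a bootstrap that resamples subjects. State that the target is the population mean change, and say how age, region and gender classes are weighted, since equal weights do not give the average over the enrolled children. Report the protocol's paired t-test (mean change, CI from SD/√n) as a pre-specified sensitivity analysis, or restore it as primary, and amend Section 5 to match.

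The cost is SAP wording and a few lines of code. The model-based CI widens by a factor 1/k: about 8–10% at R² 0.25 (1/0.93 to 1/0.905) and 21–29% at R² 0.5 (1/0.824 to 1/0.775), for D = 2.11 and 1.51. If the paired t-test becomes primary, power at the planning values is 99.9% with 70 evaluable subjects and 96.7% with 42.

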# **DOCUMENT HISTORY**

Version	Date	Modification
Final v1.0	27-DEC-2018	N/A
	_	N/A  - Typo corrected in abbreviations section on ATC. N/A added Tables 4, 5 and 6: Last category extended to include 18 years. Indeed, we may have subjects enrolled at less than 18, but aged of 18 years during the study. Footnote added Section 3.2: missing compliance added on the first programmable protocol violation Section 4.2.6: Last category for the age at randomisation extended to include 18 years. Indeed, we may have subjects enrolled at less than 18, but aged of 18 years at the time of randomisation Sections 4.2.8.1 and 4.2.8.2: Precisions added on the derived analysis visits (applying windowing as defined in section 4.2.9) to be used Section 4.2.8.4: Imputation rule added if value > X for laboratory parameters Section 4.2.9: Column "Analysis visit" added to be consistent with the reference in sections 4.2.8.1 and 4.2.8.2. Precisions added on the CRF visits to be used to derive "End of stage 1" and "End of stage 2" for safety analysis, and the fact that the last non missing assessment collected in each period will be reported under "End of Stage 1" and "End of Stage 2" Section 4.6: Details added on the compliance calculation for Stage 1 and Stage 2 Section 4.7: details added regarding conversion factor to convert mmol/L into mg/dL for serum phosphorus Section 4.9.1: Slashes removed from System/Organ/Class in order to be system organ class. Addition of AE table by SOC and PT, and by age Section 4.9.2: details added for the derivation of an episode of sustained hypercalcaemia Section 4.9.3: Formula added to derive Transferrin Saturation (%) laboratory parameter. Unsaturated Iron Binding Capacity parameter added in Table 10 Section 7.1: Numbering updated in AE section due to duplicate numbering. Addition of 2 tables related to Serum total corrected calcium (Table 14.4.3.1 and 14.4.4.1), numbering updated on the Calcium-Phosphorus product tables. Addition of 2 tables related to TEAE by SOC and PT, and by Age (Table 14.3.1.30 and 14.3.1.31) Section 7.2: Addition of list
Final v3.0	20-MAR-2019	more than one batch was used. Numbering updated on Listing 16.1.6.2 to become Listing 16.1.6.3.  - Addition of updates detailed in the SAP Addendum dated of 22
1 11141 VJ.U	20-111/AIX-2017	February 2019:

- Section 4.2.8.5: imputation of missing or partial dates on disease history
- Section 4.6: addition of new exposure to study drug tables by age group

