- with any treatment-emergent adverse events by intensity assessed by investigator (mild, moderate, severe),
- with any treatment-emergent adverse events by age at randomisation (0-<2, 2-<6, 6-<12, 12-<=18). The denominator will be the number of patients in each age group category,
- with any treatment-emergent adverse event of special interest (listed in Table 8 below),
- with any serious treatment-emergent adverse event,
- with any serious treatment-related treatment-emergent adverse event,
- with any serious treatment-emergent adverse event that led to death,
- with any non-serious treatment-emergent adverse event,
- with any treatment-emergent adverse events that led to study drug discontinuation,
- and with any treatment-emergent adverse events started <4 weeks (<1 weeks, 1-<2 weeks and 2-<4 weeks will also be presented for more granularity), 4 to <12 weeks, 12 to <24 weeks, ≥24 weeks. The denominator is the number of patients at risk at the beginning of

the period (excluding those who have withdrawn or completed); i.e. in the category 2-<4 weeks, the denominator will include patients at risk/active at week 2.

Related events include Events with Certain or Probably/Likely or Possible as causality assessed by the investigator. Unrelated events include unlikely or unrelated as causality assessed by the investigator.

 Table 8
 Adverse Event of special interest definition

Events of special interest	MedDRA
Diarrhoea	MedDRA PT: -Diarrhoea
Potential of iron accumulation	MedDRA PT: -Cardiac iron overload -Haemochromatosis -Haemosiderosis -Hereditary haemochromatosis -Hepatic siderosis -Iron overload -Pulmonary haemosiderosis -Superficial siderosis of central nervous system
Masking of GI bleeding due to discoloured stool	MedDRA PT: -Faeces discoloured MedDRA SMQs: -SMQ GI haemorrhage
Events, which could be linked to (deficiencies in) growth and skeletal development and review of bone markers	SOC: Musculoskeletal and connective tissue disorder -HLT: Bone disorders NEC (from HLGT Bone disorders (excl congenital and fractures)) -HLT: Metabolic bone disorders NEC (from HLGT Bone disorders (excl congenital and fractures)) -HLGT: Fractures  SOC: Metabolism and nutrition disorders -HLT: Bone metabolism disorders (HLGT: Bone, calcium, magnesium and phosphorus metabolism disorders) -HLT: Calcium metabolism disorders (HLGT: Bone, calcium, magnesium and phosphorus metabolism disorders)

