#### 4.9.3. Laboratory Data

Clinical laboratory values will be expressed using SI units.

The actual value and change from baseline will be summarised for each clinical laboratory parameter at each time point by treatment group based on central laboratory measurements. For serum phosphorus, calcium (total and corrected) and albumin chemistry parameters, both central and local laboratory summary tables will be provided.

Shift tables from baseline to each post-baseline visit will be produced using the low/normal/high classification based on laboratory reference ranges.

The normal ranges of some parameters from the central laboratory data are only available for the age group above or equal to 18 years and not from 0 to 17yrs; therefore shift tables will not produce for the below parameters due to missing normal ranges. Only Actual Values and Changes Over Time tables and listings will be presented.

- Ferritin
- Osteocalcin
- Transferrin
- Vitamin A
- Vitamin E
- Vitamin K
- Intact parathyroid hormone
- Fibroblast growth factor 23
- Tartrate-resistant acid phosphatase 5b
- Atypical lymphocytes and Lymphocytes atypical/leukocytes

All laboratory data will be provided in data listings.

A subset listing will be presented for all abnormal laboratory values.

**Table 10** List of Laboratory Parameters

Category	Parameters
Haematology	Erythrocytes, Mean corpuscular volume, Mean corpuscular haemoglobin
	Mean corpuscular haemoglobin concentration, Haemoglobin, Haematocrit
	Reticulocyte count, White blood cells, White blood cell differential (% and absolute value), Neutrophils, Eosinophils, Basophils, Lymphocytes, Monocytes, Platelets
Chemistry	Calcium (total, corrected), Intact parathyroid hormone (only shift tables as already summarised as part of the secondary safety endpoints), Creatinine, Glucose, Triglycerides, Total protein, Albumin, Urea, Uric acid, Total bilirubin, Total cholesterol (differential in high density lipoproteins and low density lipoproteins), Creatine phosphokinase, C-reactive protein, Bicarbonate, Sodium, Potassium, Chloride
Chemistry – Liver Enzymes	Alkaline phosphatase, Aspartate transaminase, Alanine transaminase, Lactate dehydrogenase, Gamma-glutamyl transpeptidase
Iron Status Parameters	Iron, Ferritin, Transferrin, Unsaturated Iron Binding Capacity, Transferrin saturation
Vitamins	A, 25(OH)D, 1,25(OH)2D, E, K
Bone Markers	Carboxyterminal cross-linking telopeptide of bone collagen,

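### Transferrin saturation (TSAT) is dropped although it can be derived from the iron and UIBC already collected, and Table 10 still lists it

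*SAP*

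**What the plan says.** Section 5 (Changes to Planned Analyses) names four iron parameters required by the protocol: iron, ferritin, transferrin and TSAT. It then names the four assessed in the study: iron, ferritin, transferrin and UIBC. It calls UIBC a surrogate for TSAT that "has been reported to identify 100% of iron overloaded patients and 95% of patients with normal iron stores". It goes on: "The use of UIBC instead of TSAT is estimated to have no impact on the reliability of safety assessments in this clinical study". It ends: "Therefore, TSAT will not be derived and presented". A Note to File is mentioned.

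Section 4.9.3 (Laboratory Data) commits to actual values and changes from baseline for every clinical laboratory parameter, using central laboratory data. Its Table 10 gives the iron status parameters as "Iron, Ferritin, Transferrin, Unsaturated Iron Binding Capacity, Transferrin saturation". The text of Section 4.9.3 makes no exception for TSAT.

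Blood iron parameters are among the secondary safety endpoints (Section 2.5.3.2). The events of special interest in Table 8 (Section 4.9.1) include "Potential of iron accumulation", and the same section converts PA21 doses to mg of iron.

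**The concern.** UIBC is the unoccupied part of the binding capacity. Saturation is the occupied share, so it depends on iron as well as on UIBC. With both in the database, choosing UIBC in place of TSAT is unnecessary, because the two can be reported side by side.

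The stated rationale does not close the gap. The two percentages carry no citation, and none of the five titles in Section 6 concerns UIBC. They describe separating iron overload from normal stores and say nothing about low iron or change over time. Such a classification also needs a cut-off, and the SAP sets none for UIBC.

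At stake is a protocol-specified descriptive safety measure for an iron-based drug in children. In addition, Section 4.9.3 and Section 5 give a programmer opposite instructions about the same parameter.

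**Working it through.** The plan has no figure to reproduce here. There are two checks.

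**1. Can TSAT be derived?**
- Needed: iron and UIBC from the same sample, in the same molar unit.
- Available: Section 5 says both were assessed, and Table 10 places both under iron status.
- Formula (standard definition, an assumption because the current SAP does not print it): TSAT (%) = 100 x iron/(iron + UIBC).
- Corroboration: the Document History records, for a superseded SAP version, "Formula added to derive Transferrin Saturation (%) laboratory parameter", with UIBC added to Table 10 at the same revision. This is used only as evidence of feasibility. That the log differs from the current text is not an error.

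**2. Do separate summaries of iron and UIBC already give the same information?** Take two hypothetical groups of two subjects each (assumed values in umol/L, not trial data):

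| Group | Subject | Iron | UIBC | TSAT |
|---|---|---|---|---|
| A | 1 | 10 | 40 | 10/50 = 20.0% |
| A | 2 | 30 | 20 | 30/50 = 60.0% |
| B | 1 | 10 | 20 | 10/30 = 33.3% |
| B | 2 | 30 | 40 | 30/70 = 42.9% |

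- Iron is {10, 30} in both groups: mean 20, minimum 10, maximum 30.
- UIBC is {20, 40} in both groups: mean 30, minimum 20, maximum 40.
- Every summary statistic of iron and of UIBC is therefore the same in A and B.
- TSAT differs. The maximum is 60.0% against 42.9%. The range is 60.0 - 20.0 = 40.0 points against 42.9 - 33.3, about 9.5 points.

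Now read A as baseline and B as follow-up in the same two subjects:
- Iron changes by 0 in both.
- UIBC changes by -20 and +20, mean 0.
- TSAT changes by 33.3 - 20.0 = +13.3 points and 42.9 - 60.0 = -17.1 points, mean -1.9.

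So the separate summaries give neither the distribution of saturation nor its change. Which iron value goes with which UIBC value is lost once each is summarised alone.

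**The case against.** The case for leaving the plan as it stands has substance.

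- **The change is disclosed.** It appears in Section 5 with a rationale, an impact statement and a Note to File. That note is not available, so a further reason may exist. This stands: a reader might infer that a safety measure is being withheld, and the SAP does not support that.
- **UIBC does not stand alone.** A reader might infer that it is the only iron measure left, so that subjects with equal UIBC and different iron could not be told apart. That is wrong. Iron, ferritin, transferrin and UIBC all fall under Table 14.4.7.6 and Listing 16.2.8.5. Iron and UIBC are also absent from the list of parameters without shift tables. What is lost is only the per-subject ratio in the group summaries, and even that can be worked out by hand from the listing.
- **No event count depends on TSAT.** A reader might fear that iron accumulation events would be missed. Table 8 defines them entirely by MedDRA preferred terms, so no laboratory value enters.
- **A surrogate need not determine what it replaces.** True, but it should then rest on evidence that can be checked, and no source is given. The question of a surrogate arises only where the original measure is unobtainable, and here it is not.
- **Table 10 is a leftover.** Probably so: the Document History logs the decision not to derive TSAT against Section 4.9.3. Deleting the entry would end the contradiction but would not restore the measure.

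The remaining iron data are also thinner than they look. Section 4.9.3 gives ferritin and transferrin no shift tables, for want of paediatric reference ranges. Table 3 excludes ferritin under 36 months of age unless it is routinely available, and does not schedule it at Visit 13, where the other iron parameters are due.

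**Conclusion.** The point holds in a limited form. The SAP drops a protocol-specified measure that its own data can supply, on an uncited claim, and its current text is inconsistent about whether the measure is reported.

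The loss is the distribution of, and change in, per-subject saturation in the descriptive safety tables. Its size in this trial cannot be stated. The worked values are assumed, and the SAP gives no TSAT threshold against which to judge a difference. Efficacy results, analysis populations and adverse-event counts are unaffected.

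The conclusion assumes the standard definition of TSAT, and that iron and UIBC are available from the same central sample.

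**What to change.** 1. In Section 4.9.3, define TSAT (%) = 100 x iron/(iron + UIBC), computed only where both central values come from the same sample and share a molar unit.
2. Report actual values and change from baseline in Table 14.4.7.6 beside UIBC, and values in Listing 16.2.8.5.
3. Replace the closing statement in Section 5 with one saying that TSAT is derived from iron and UIBC, so that it agrees with Table 10. Cite the source of the two percentages or remove them.

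No shift table is requested, since the SAP does not show that a paediatric reference range for TSAT exists. The cost is one derived variable in an existing table and listing, with no new samples.

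If the sponsor has a documented reason not to derive TSAT, the minimum is to state it in Section 5, cite the UIBC evidence and delete TSAT from Table 10.
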